7.2.12 Tumor Measurement

Tumor assessments/imaging studies of the chest, abdomen, and pelvis (as clinically indicated) must be obtained at each time point listed below for all patients.

- Baseline within 28 days prior to Day 1 Cycle 1
- Every 8 weeks from the start of treatment
- Within 2 weeks of the End of Treatment Visit if the patient has discontinued treatment for reasons other than radiologic disease progression. If an End of Treatment visit is not performed, tumor measurements must be obtained at the time the patient is discontinued from treatment.
- For patients that discontinued treatment for reasons other than radiologic progression, every 8 weeks during the follow-up period until the patient develops radiologic progression or the start of new anticancer treatment.

On-site tumor assessments will be performed by the Investigator/local radiologist according to RECIST criteria (version 1.1). Results of these assessments including response for target and non-target lesions and appearance of new lesions will be the basis for the continuation or discontinuation of study medication.

If the Investigator determines that a patient develops clinical progression manifested by symptomatic deterioration but not supported by radiologic evidence of progression, the patient should stop treatment. Symptoms of clinical progression must be documented in the patient's source documents. Every effort should be made to document objective progression even after discontinuation of treatment.

If a patient is withdrawn due to radiologic disease progression, additional CT scans are not required at the End of Treatment Visit. The same method of assessment and the same technique must be used to characterize each identified and reported lesion at Baseline, throughout the study, and during the follow-up period.

All patients' files and radiological assessments must be available for source verification. Results of any unscheduled evaluations should be recorded.

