7.3 Outcome Measures

7.3.1 Primary Outcome:

- **16-week progression-free survival (PFS) rate:** The percentage of study population alive and without progression (according to RECIST 1.1) at 16 weeks from the date of informed consent

7.3.2 Secondary Outcomes:

- **Progression-free Survival (PFS):** PFS is measured from the date of informed consent to radiographically documented progression according to RECIST 1.1 or death from any cause (whichever occurs first). Participants alive and without disease progression or lost to follow-up will be censored at the date of their last radiographic assessment
- **Time to progression (TTP):** TTP is measured from the date of informed consent to radiographically documented progression according to RECIST 1.1. Participants death and without disease progression, alive without disease progression, or lost to follow-up will be censored at the date of their last radiographic assessment
- **Overall survival (OS):** OS is measured from date of informed consent to the date of death from any cause. Participants alive or lost to follow-up will be censored at the date of their last radiographic assessment
- **Objective response rate (ORR):** The percentage of patients with radiologically complete or partial response as determined by the Investigator according to RECIST version 1.1.
- **Disease control rate (DCR):** The percentage of patients with radiologically complete response, partial response, or stable disease as determined by the Investigators according to RECIST version 1.1
- **Duration of response (DoR):** DoR is the time from documentation of tumor response to radiographically documented disease progression
- **Time to deterioration of ECOG performance status:** Time from date of informed consent until the first date on which ECOG performance status score of 2 or higher was recorded ⁽³⁶⁻³⁷⁾
- **Time to deterioration of quality of life:** Decrease from baseline of 10 points or more on the EORTC QLQ-C30 maintained for two consecutive assessments or a decrease of 10 points or more in one assessment followed by death from any cause within 3 weeks.
- **Safety outcome measures:** Incidence, nature, and severity of adverse events graded according to NCI-CTCAE v5.0

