7.4 Criteria for Removal from Protocol Treatment

- RECIST-defined disease progression
- Clinical progression
- Patient experiences an irreversible, treatment-related, Grade 4, clinically relevant, non-hematologic event.
- Inter-current disease that would affect assessments of clinical status to a significant degree, require discontinuation of drug, or both.
- Unacceptable adverse events, or change in underlying condition such that the patient can no longer tolerate therapy, including:
 - (a) A maximum dose delay >28 days from the scheduled start date of the next cycle.
 - (b) Need for more than 3 dose reductions of study medication
- Physician's decision including need for other anticancer therapy not specified in the protocol or surgery or radiotherapy to the only site(s) of disease being evaluated in this protocol
- Patient's request irrespective of the reason

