Appendix 1. STUDY SCHEDULE

	Baseline Period		On Treatment Period (+/-3 days for procedures; +/-7 days for CT scans & FU)							End of Treatment Period (q8wk)		
	Baseline Day		Cycle 1				Subsequent Cycles			End of Treatment	30-day Safety FU	Survival FU
	-28 to -1	-7 to -1	1	12	15	End of recovery	1	12	15			
Procedure	x											
Sign ICF	x											
Enrolment	x											
Medical History	x											
Physical Examination		x					x			x	x	
Baseline signs and symptoms	x											
ECG	x											
Vital signs, height, body weight		x					x			x	x	
ECOG performance status	x		x				x			x	x	
Hematology		x			x		x		x	x	x	
Serum chemistry		x			x		x		x	x	x	
CA 19-9		x			x		x		x	x	x	
Urinalysis		x										
Pregnancy Test		x										
Tumor measurement	x								x	x		x
Concomitant Medications	x	➔	➔	➔	➔	➔	➔	➔	➔	➔	➔	➔
AE / SAE assessment		x	➔	➔	➔	➔	➔	➔	➔	➔	➔	➔
Survival status		x	➔	➔	➔	➔	➔	➔	➔	➔	➔	➔
Quality of life assessment		x										
Exploratory biomarker	x		x				x					
TAS-102 treatment			x (D1-5)	x (D8-12)			x (D1-5)	x (D8-12)				

Footnotes:

- (1) Sign ICF: Written informed consent should be obtained prior to the performance of any study procedure
- (2) Vital Signs: Heart rate, blood pressure, body temperature, respiratory rate; collect at the start of every cycle; collect within 24 hours prior to Day 1 study drug administration.
- (3) Blood tests within 28 days prior to study assessment include complete blood count, liver function test, renal function test, eGFR, coagulation profile & hepatitis B status.
- (4) Tumor Measurements: Obtain a contrast-enhanced computed tomography (CT) scan of the chest and abdomen (and pelvis, if clinically indicated) within 28 days prior to Day 1 of Cycle 1 and **every 8 weeks thereafter** during study treatment. If a patient discontinues treatment due to radiologic disease progression, additional tumor assessment is not required at the End of Treatment visit. For patients who discontinue treatment for reasons other than radiologic disease progression, every effort should be made to perform an end of treatment tumor assessment prior to the start of new anticancer therapy. Patients that discontinued treatment for reasons other than disease progression should continue to be followed for tumor response every 8 weeks until the patient develops radiologic disease progression (or death) or initiation of new anticancer therapy.

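### PFS counts a death at any time after new anticancer therapy although scanning has stopped, so patients who switch before week 16 and die later are carried as progression-free in the Kaplan-Meier estimate

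*Protocol*

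**What the plan says.** **Event and censoring.** Protocol 7.3.2 runs PFS from consent to "radiographically documented progression according to RECIST 1.1 or death from any cause (whichever occurs first". Its only censoring rule is "Participants alive and without disease progression or lost to follow-up will be censored at the date of their last radiographic assessment". Neither sentence mentions new anticancer therapy. The primary outcome in 7.3.1 is the share of patients alive and without RECIST progression 16 weeks after consent. Section 9.1 estimates that share by Kaplan-Meier, expressed on the exact binomial distribution.

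**Leaving treatment without a PFS event.** Section 7.2.12 foresees "clinical progression manifested by symptomatic deterioration but not supported by radiologic evidence of progression, the patient should stop treatment". Section 7.4 also lists "Physician's decision including need for other anticancer therapy not specified in the protocol" as a reason for removal.

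**Scanning.** For patients who stop for reasons other than radiologic progression, 7.2.12 schedules scans "every 8 weeks during the follow-up period until the patient develops radiologic progression or the start of new anticancer treatment". Appendix 1 footnote 4 gives the same end point: "until the patient develops radiologic disease progression (or death) or initiation of new anticancer therapy". A scan at discontinuation is mandatory in 7.2.12, either within 2 weeks of the End of Treatment Visit or, without such a visit, at discontinuation. Footnote 4 asks that "every effort should be made to perform an end of treatment tumor assessment prior to the start of new anticancer therapy".

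**Deaths and later therapy.** Section 7.2.19 collects survival status every 8 weeks. Section 7.2.13 collects the time of starting new anticancer therapy at the 30-day visit, and anticancer therapies during survival follow-up.

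**The concern.** The event definition and the scanning schedule do not fit together. Once new therapy starts, no further scheduled scan can show progression, but death remains a PFS event however late it comes. The interval between the switch and the death, spent on another drug, is counted as progression-free time on TAS-102.

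The rule is also asymmetric. The patient who dies months later gets the long PFS time, and the patient who lives is cut back to the last scan. Status at week 16 should be settled by what is known around week 16. Here it can turn on an event long afterwards, under a different treatment.

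The Kaplan-Meier 16-week rate is the primary estimate of a single-arm trial with no control group to share the distortion. Median PFS, the first secondary objective, uses the same rule.

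**Working it through.** **1. The design's own figures.** Section 9.3 gives p0 = 0.10, p1 = 0.30, 25 evaluable patients and a bar of 6. By exact binomial, P(X ≥ 6 | 25, 0.10) = 0.0334 and P(X ≥ 6 | 25, 0.30) = 0.8065. With 10% dropout, 25 / 0.9 = 27.8, rounded up to 28. The stated design reproduces.

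**2. One patient under the written rule** (assumed course; weeks from consent, taken for simplicity as the first day of treatment). Stable at the week-8 scan, clinical progression at week 10, clean discontinuation scan that week, another regimen from week 11.
- Dies at week 40: PFS is 40 weeks with an event, so progression-free at week 16.
- Alive at cut-off: censored at week 10, or at week 8 if the discontinuation scan was missed.

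**3. Twenty-five patients** (assumed). Events: 4 deaths at week 6, 13 progressions at week 8 and 2 at week 15. Three patients are progression-free past week 16, and 3 switch at week 11. The estimate is S(16) = product of (1 − d/n) over event times up to week 16.

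| Coding of the 3 switchers | S(16) | Result |
|---|---|---|
| Die at week 40 | 21/25 × 8/21 × 6/8 | 24.0% |
| Alive, censored at last scan | 21/25 × 8/21 × 3/5 | 19.2% |
| New therapy at week 11 is failure | 21/25 × 8/21 × 5/8 × 3/5 | 12.0% |

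In the second row the 3 patients are still at risk at week 8 and gone by week 15. No event falls between weeks 8 and 10, so censoring at week 8 (scan missed) or week 10 (scan clean) gives the same 19.2%. The contrast does not need a missed scan.

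**4. Varying the number of switchers** (second assumed set of 25). Four patients are progression-free past week 16, 5 have events at week 12, m switch at week 9 after a clean week-8 scan, and the rest have events at week 8.

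| m | Die later | Alive, censored | New therapy is failure |
|---|---|---|---|
| 1 | 20.0% | 17.8% | 16.0% |
| 2 | 24.0% | 19.6% | 16.0% |
| 3 | 28.0% | 21.3% | 16.0% |
| 4 | 32.0% | 23.1% | 16.0% |

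For m = 1 the terms are (4 + 1)/25, then 10/25 × 4/9, then 4/25. Compared with failure, each later death adds 1/25 = 4 percentage points.

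**5. Median PFS.** In step 3, S(8) = 8/25 = 32%, so the median is week 8 under every coding. In step 4 it moves only for m = 4: week 12 if the switchers die later or are censored, week 9 if new therapy is failure. The rule can lengthen the median but need not.

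**The case against.** **Scans do not simply cease when treatment stops.** 7.2.12 requires a discontinuation scan and asks for continued effort to document objective progression afterwards. Under 7.2.17, a decision within 2 weeks of the last treatment visit needs no End of Treatment Visit, so the scan is then due at discontinuation. A reader might infer that a clinical progressor gets no further scan; the documents do not support that. This narrows the group to patients whose discontinuation scan is clean or missed and who then switch before week 16. It does not empty it, and step 3 holds with a clean scan.

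**The go/no-go decision may be untouched.** It is tempting to infer an inflated type I error: if 2%, 5% or 10% of would-be failures were counted as progression-free, P(at least 6 of 25) at a true 10% would go from 0.033 to 0.066, 0.144 or 0.335. That does not follow. Section 9.3 excludes and replaces patients who drop out before they can be assessed and does not say whether switching is dropping out. If it is, later death cannot change the count. The percentages are also assumed.

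**The frequency is unknown.** No section gives the rate of early switching. The median OS of 3.3 to 9.9 months in section 1.1 suggests that many switchers would die during follow-up, but says nothing about how many patients switch.

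**The censoring rule stands under secondary PFS, and a SAP may exist.** True. But 7.3.1 has no rule of its own, a Kaplan-Meier estimate needs one, and 7.3.2 holds the only PFS rule. This is a stated rule with a poor consequence, not detail left open. Section 9.2 calls for a protocol amendment if the primary endpoint or its methods change.

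**Ignoring new therapy can be legitimate.** It can, if progression is still assessed after the switch. Here scheduled scanning ends.

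**Conclusion.** The point stands for the Kaplan-Meier analyses. Followed as written, the protocol credits survival time on another therapy as progression-free time for switchers who die, and cuts switchers who live back to their last scan. Compared with counting new therapy as failure, the 16-week rate can only go up, by 4 percentage points per such patient in 25; median PFS may rise or stay put. Compared with censoring at the last scan, the 16-week rate is again higher, by 4.8 points in the 3-of-25 example (24.0% against 19.2%).

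These sizes rest on assumed numbers and timings and on applying the 7.3.2 rule to the primary Kaplan-Meier estimate. The documents do not support a stated error rate for the 6-of-25 rule, a claim that early switching is common, or a claim that failure is the only acceptable coding of new therapy.

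**What to change.** - In 7.3.1 and 7.3.2, state one rule for new anticancer therapy before documented progression, under which a death after new therapy no longer sets the PFS time. For example: not progression-free at week 16, with PFS ending as an event at the start of new therapy, and censoring at the last scan before new therapy as the sensitivity analysis. The reverse order is also acceptable.
- Apply the same rule in the 9.3 count, so that it is clear whether a switcher is a failure or non-assessable.
- Reconcile 7.2.12 and Appendix 1 footnote 4 on the timing of the discontinuation scan relative to new therapy.

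**Cost.** An amendment of wording and one sensitivity analysis. Anticancer therapies are already collected under 7.2.13; confirm that start dates are also recorded after the 30-day visit. The reported 16-week rate and median PFS may be lower, and not always slightly: the 3-of-25 example halves the rate, from 24.0% to 12.0%. The failure rule also counts patients who switch for toxicity or by request, which moves the endpoint toward treatment failure. Censoring avoids that but treats clinical progressors as if they resembled patients still being scanned. Hence both should be reported.

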2.4 Study Participants

A total of 28 patients will be accrued to assess the potential benefit of TAS-102.

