5.4 Registration Guidelines

- All the patients must be registered with the Investigator(s) prior to initiation of treatment
- Forms A (registration) and B (consent) will be submitted
- The registration desk will confirm all eligibility criteria and obtain essential information (including patient number)

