9.3 Sample Size Calculation

H0: The null hypothesis is that the 16-week PFS rate of 10% is similar to historical results.

H1: The alternative hypothesis of treatment efficacy: experimental treatment with TAS-102 would result in 16-week PFS rate of 30%.

To detect 20% of differences from 10% to 30% in the 16-week PFS rate, with Type I error of 0.05 and 80% power, and assuming 10% drop out rate, the target sample size is 28 patients.

The null hypothesis will be rejected if 6 or more out of first 25 evaluable patients are progression-free and alive at 16 weeks, the treatment will be considered worthy of further investigation. Otherwise, if 5 or fewer patients were progression-free and alive at 16 weeks in the 25 evaluable patients, this regimen would have been considered ineffective in this patient population.

Patients may drop out before their 16-week PFS rate can be assessed. Such patients will be excluded for the primary endpoint assessment and will be replaced by other patients that 16-week PFS rate can be assessed. We assume 50% of screened population will be eligible for the study, thus we plan to screen for 56 patients.

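### Overall survival is timed from informed consent, but patients enter the study population only at a later registration, so the consent-to-registration interval counts as guaranteed survival time

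*Protocol*

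**What the plan says.** Section 7.3.2 fixes the start of the OS clock: "OS is measured from date of informed consent to the date of death from any cause". Sections 7.3.1 and 7.3.2 use the same origin for the 16-week PFS rate, PFS, TTP and time to ECOG deterioration.

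Consent is the first step of screening. Appendix 1, footnote 1, reads "Written informed consent should be obtained prior to the performance of any study procedure", and the schedule puts signing of the consent form in the Day -28 to -1 column. Section 7.2.12 gives the same outer limit for the baseline scan: "Baseline within 28 days prior to Day 1 Cycle 1".

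Entry comes later. Section 5.4 says "All the patients must be registered with the Investigator(s) prior to initiation of treatment" and, of that step, "The registration desk will confirm all eligibility criteria and obtain essential information (including patient number".

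The population is the set of patients who got through. Section 2.4: "A total of 28 patients will be accrued to assess the potential benefit of TAS-102". Section 9.3: "We assume 50% of screened population will be eligible for the study, thus we plan to screen for 56 patients".

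The protocol states no delayed-entry (left-truncation) adjustment and no OS analysis from registration or first dose.

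**The concern.** A patient who consents and then dies, or is no longer eligible, before registration is a screen failure and not one of the 28. Death between consent and registration therefore cannot be observed in the analysed group, yet the definition adds that interval to every analysed patient's survival. This is immortal time.

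Its size depends on how long a site takes to move patients from consent to registration, and not on TAS-102. Median OS is a listed secondary objective (section 2.2). In a single-arm trial the estimate has no internal comparator that would carry the same shift.

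**Working it through.** **The plan's own figures.** No sample size, power or target is stated for OS, so there is no OS figure to reproduce. The design figures in section 9.3 do reproduce. With 25 evaluable patients and success at 6 or more, the exact binomial gives a one-sided type I error of 0.0334 at 10% and power of 0.8065 at 30%. Then 25 / 0.9 = 27.8, rounded up to 28, and 28 / 0.5 = 56 screened. None of these uses OS.

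**Inputs**
- Origin: consent (7.3.2).
- Gate: registration, with all eligibility criteria confirmed, before treatment (5.4).
- Window: up to 28 days before Cycle 1 Day 1 (Appendix 1).
- Consent-to-registration lag L: not stated. Assumed values are 7, 14 and 28 days; 28 is the limit of the window.
- Reference medians: 6.1 months (the liposomal irinotecan combination in section 1.1), and 3.5 and 7.6 months (lowest and highest in Table 2). They only set a scale.

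**Formula.** If every registered patient has the same lag L, then

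median from consent = median from registration + L.

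This needs no assumption about the shape of the survival curve. With 365.25 / 12 = 30.4375 days per month:

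- 7 / 30.4375 = 0.23 months
- 14 / 30.4375 = 0.46 months
- 28 / 30.4375 = 0.92 months

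| Median from registration | L = 7 days | L = 14 days | L = 28 days |
|---|---|---|---|
| 3.5 months | 3.73 (+6.6%) | 3.96 (+13.1%) | 4.42 (+26.3%) |
| 6.1 months | 6.33 (+3.8%) | 6.56 (+7.5%) | 7.02 (+15.1%) |
| 7.6 months | 7.83 (+3.0%) | 8.06 (+6.1%) | 8.52 (+12.1%) |

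**Check by simulation.** One million exponential survival times were drawn with a median of 6.1 months from consent. Only patients alive at the end of the lag were kept.

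| Lag | Alive at gate | Median from consent, all consenters | Median from consent, entrants | Median from gate, entrants |
|---|---|---|---|---|
| 14 days | 0.949 | 6.10 | 6.56 | 6.10 |
| 28 days | 0.900 | 6.10 | 7.02 | 6.10 |
| Uniform 1 to 28 days | 0.948 | 6.09 | 6.56 | 6.09 |

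Timing entrants from consent is the only one of the three medians that is shifted. Counting all consenters from consent, or entrants from the gate, both return the true value under a constant hazard.

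**The case against.** Several objections limit the point.

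- **The gate is registration, not first dose.** A reader might infer that every analysed patient is guaranteed to survive until treatment starts. The documents do not support that. A patient registered but dead before Day 1 has been accrued, and that death counts in OS; section 9.3 excludes and replaces drop-outs only for the primary endpoint. Appendix 1 also lists enrolment in the same Day -28 to -1 column as consent, so the guaranteed interval may be short. On the other hand, 7.2.9 places baseline bloods in the last 7 days before Day 1, so registration may also fall late. The protocol does not settle it.
- **The lag is assumed.** The 28-day figures are an upper limit, not an expectation. The 50% in section 9.3 concerns eligibility and says nothing about duration or about deaths during screening.
- **Net direction.** A reader might infer that reported OS will be too long overall. The same definition says "Participants alive or lost to follow-up will be censored at the date of their last radiographic assessment", and for OS that pulls the estimate down. The balance depends on how many patients are alive at the end. One flaw does not cure the other, but only the time-origin component is shown to be upward.
- **Outside comparison.** It is tempting to set 0.92 months against the 1.9-month gain (6.1 vs 4.2) in section 1.1. That gain is a difference between randomised arms and is no yardstick for a shift in one arm's median. The protocol sets no OS benchmark and does not give the time origins of the studies in Tables 1 and 2, so the bias relative to them cannot be computed.
- **Importance.** OS is secondary and has no target. With 28 deaths and an exponential median of 6.1 months, an approximate 95% interval is 6.1 × exp(±1.96/√28), or 4.2 to 8.8 months. A shift of about half a month is small beside that. Still, it is systematic and easy to avoid.

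If all 56 consenters were analysed the effect would vanish, but sections 2.4 and 9.3 describe a study population of 28.

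**Conclusion.** The point holds for the time origin. OS as defined in 7.3.2 credits the registered patients with an interval in which they could not have died and remained in the study population. The effect on the median is upward by the consent-to-registration lag: 0.23, 0.46 or 0.92 months for assumed lags of 7, 14 or 28 days, about 4%, 8% or 15% of 6.1 months.

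This rests on two assumptions: the lag, which the protocol does not state, and an OS analysis set made up of the accrued patients rather than everyone who consented. It is not a claim about the net bias of the OS estimate, and it does not touch the go/no-go rule through OS. It warrants a change to the definitions, not to the sample size.

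**What to change.** In 7.3.1 and 7.3.2, use one common origin for OS, PFS, TTP, the 16-week PFS rate and time to ECOG deterioration. Either of these works:

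- **Registration, for all registered patients.** This keeps patients who are registered but never dosed.
- **Cycle 1 Day 1, for all treated patients.** This matches the scan schedule in 7.2.12, which runs from the start of treatment.

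Alternatively, keep consent as the origin and let patients enter the risk set at registration (delayed entry). With 28 patients the earliest risk sets would be small and the curve unstable there.

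Moving OS alone is not enough. If PFS stayed on consent, a patient who dies without progression would have a PFS time longer than the OS time. Report the consent-to-registration and consent-to-first-dose intervals descriptively.

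Cost: several definitions change, including the primary one, so section 9.2 calls for a protocol amendment before any analysis. The reported medians become slightly less favourable. The 25, 28 and 56 stay as they are.

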4 STUDY SCHEMA

Safety monitoring will begin at the time the Informed Consent Form (ICF) is signed and continue for 30 days after the last dose of study medication or until the initiation of another cancer therapy, whichever comes first.

At the end of treatment, all patients will be followed for survival at scheduled 8-week time intervals until 2 years.

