7.2.19 Survival Follow-up after 30-Day Safety Visit

All patients will be followed for survival status (alive/dead) at scheduled 8-week ($+/ - 7$ days) time intervals until death. Patients will be followed until 12 months after the first dose of study medication for the last patient randomized, even if consent for study participation has been withdrawn. The Investigator should make every effort to contact the patient or primary caregiver to determine his/her survival status. Times and dates of contact must be documented in the patient's records.

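### Overall survival is censored at the last scan, although scanning stops at progression and survival contact continues, so the OS estimate is biased downward

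*Protocol*

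**What the plan says.** Protocol section 7.3.2 defines the OS event without any time limit: "OS is measured from date of informed consent to the date of death from any cause". The censoring rule follows: "Participants alive or lost to follow-up will be censored at the date of their last radiographic assessment". It names the same censoring date as the PFS rule a few lines above: "Participants alive and without disease progression or lost to follow-up will be censored at the date of their last radiographic assessment".

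Scanning and survival follow-up run on different clocks:

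- **Scans (section 7.2.12).** The interval is "Every 8 weeks from the start of treatment". Patients who stop treatment for reasons other than radiologic progression are scanned "every 8 weeks during the follow-up period until the patient develops radiologic progression or the start of new anticancer treatment". After radiologic progression no further scan is required; Appendix 1, footnote 4, says the same.
- **Survival status (section 7.2.19).** "All patients will be followed for survival status (alive/dead) at scheduled 8-week" intervals until death, up to 12 months after the last patient's first dose, with contact dates documented. Section 4 gives a different length: "all patients will be followed for survival at scheduled 8-week time intervals until 2 years".

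Section 9.1 estimates OS by Kaplan-Meier. Nothing elsewhere in the protocol overrides the OS censoring rule.

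**The concern.** Last-scan censoring suits PFS and TTP, because progression status is known only up to the last scan. Vital status is learned by contact, not by CT. Under the OS rule, a patient who dies keeps all follow-up up to death, while a patient still alive loses everything after the last scan.

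The gap is long. Progression ends treatment (section 7.4), and section 1.1 cites median PFS of 1.6 to 3.8 months against median OS of 3.3 to 9.9 months. Many patients would have their last scan months before their last survival contact.

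Kaplan-Meier assumes that a patient censored at time t has the same outlook as those still at risk at t. Here, patients are censored early because they turned out to be alive later. The risk set shrinks, the deaths stay, the hazard is overstated and median OS comes out too low. The better the survival, the more patients are alive at cut-off and the larger the error.

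**Working it through.** **1. The plan's own figure.** The protocol states no OS figure. Its sample size reproduces and does not involve OS: P(X ≥ 6 | n = 25, p = 0.10) = 0.033; P(X ≥ 6 | n = 25, p = 0.30) = 0.807; 25 / 0.9 = 27.8, rounded up to 28.

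**2. Inputs.** From the protocol: 8-weekly scans (8 weeks = 1.84 months), stopping at the first scan that shows progression; follow-up to 12 months after the last entry, or 24 months per patient; medians from Tables 1 and 2. Assumed: exponential times, progression independent of death, uniform accrual over 12 months, no loss to follow-up. Scans stopping early for new therapy are not modelled.

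**3. Where the bias comes from.** Up to month 12 nobody has reached the data cut-off, so the correct risk set is S(t), the proportion still alive. The written rule removes a(t), the proportion who are alive at cut-off and had their last scan by t. The apparent hazard is the true hazard multiplied by

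S(t) / [S(t) − a(t)], with a(t) = A × P(last scan by t),

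where A is the proportion alive at cut-off.

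Take median OS 6.1 and PFS 3.1 months (liposomal irinotecan plus 5-FU/LV, Table 1), with 12 + 12 months:

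- λ = ln 2 / 6.1 = 0.1136. A = (e^(−12λ) − e^(−24λ)) / (12λ) = (0.2557 − 0.0654) / 1.3636 = 0.140.
- Month 6: the latest scan was at week 24 (5.52 months). P(last scan by then) = 1 − 0.5^(5.52/3.1) = 0.709. a = 0.140 × 0.709 = 0.099. S = 0.506. Multiplier 0.506 / 0.407 = 1.24.
- Just before month 12: the latest scan was at week 48 (11.04 months). P = 1 − 0.5^(11.04/3.1) = 0.915. a = 0.128. S = 0.256. Multiplier 0.256 / 0.128 = 2.0.

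Accumulating the inflated hazard gives a median of about 5.7 months and 12-month OS of 17%, against true values of 6.1 months and 26%.

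**4. Simulated Kaplan-Meier under both rules.**

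| True median OS / PFS (months) | Accrual + follow-up | Alive at cut-off | Median OS, as written vs last known alive | 12-month OS, as written vs last known alive |
|---|---|---|---|---|
| 4.5 / 2.0 | 12 + 12 | 7% | 4.3 vs 4.5 | 10% vs 16% |
| 6.1 / 3.1 | 12 + 12 | 14% | 5.6 vs 6.1 | 17% vs 26% |
| 6.1 / 3.1 | 24 months each | 7% | 5.9 vs 6.1 | 22% vs 26% |
| 9.9 / 2.9 | 12 + 12 | 29% | 7.8 vs 10.0 | 27% vs 43% |
| 9.9 / 2.9 | 24 months each | 19% | 8.5 vs 9.9 | 34% vs 43% |

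The second row agrees with step 3. Censoring at the date last known alive recovers the true value throughout. Assuming 10% loss to follow-up left the pattern unchanged.

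**5. Dropping independence.** With PFS median 2.0 months, 18-month accrual plus 12 months and a 24-month cap, independence gives medians of 5.5 vs 6.0 and 6.8 vs 8.0. With a correlation of 0.5 between progression and death times (Gaussian copula, assumed), they become 5.8 vs 6.0 and 7.2 vs 8.0.

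**The case against.** The best counter-argument accepts that the rule is wrong and disputes how much it matters.

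- **OS is secondary.** It carries no hypothesis, threshold or decision rule. This stands.
- **The protocol names median OS, not 12-month OS.** This also stands: the larger percentage-point shifts describe the tail of the curve. For true medians of 4.5 to 6.3 months, the median falls by only about 0.1 to 0.5 months under the planned follow-up.
- **Independence exaggerates the bias.** Long survivors tend to progress later and so have later last scans. At a correlation of 0.5 the median shift at a true median of 6 months roughly halves. The bias persists, and at a true median of 8 months it is still about 0.8 months.
- **Noise at n = 28 is larger.** In the step 5 setting with a true median of 6 months, the correctly censored median has a sampling standard deviation of about 1.7 months. That is true, but noise averages to zero and this error always points the same way.
- **Few patients are affected.** Only those alive at cut-off or lost are re-censored, and those still being scanned lose little. Unscheduled scans may also count. This limits the size.
- **Appendix 1 marks tumor measurement under survival follow-up.** Footnote 4 restricts off-treatment scans to patients who stopped for reasons other than progression, so this does not rescue the rule.

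Nor can the matter be left to the SAP. The protocol fixes the rule, so an SAP that follows it inherits the bias and one that does not contradicts the protocol.

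**Conclusion.** The concern holds. The written rule makes OS censoring depend on later survival, and it lowered the estimate in every scenario tried. With at least 12 months of follow-up after the last entry, or 24 months per patient, median OS is understated by about 0.1 to 0.5 months at true medians of 4.5 to 6.3 months, and by about 1.4 to 2.2 months at 9.9 months, the top of the range cited in section 1.1. The corresponding losses in 12-month OS are about 2 to 9 and 9 to 17 percentage points.

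The direction follows from the text alone. The size rests on assumed accrual, exponential times and independence of progression and death; positive correlation reduces it. The primary endpoint, the sample size and the 6-of-25 rule are not affected. The correction should still be made before any OS analysis, because the rule is wrong as written and the error is largest when patients live longest.

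**What to change.** In section 7.3.2, replace the OS censoring sentence with: participants not known to have died are censored at the date they were last known to be alive (last visit or survival contact, or the data cut-off if known to be alive then). Leave last-scan censoring in place for PFS and TTP.

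The cost is one sentence, made by protocol amendment before analysis, which is the route section 9.2 sets out for changes to key endpoints or their methods. No extra visits, scans or patients are needed, because section 7.2.19 already requires contact dates to be documented. In the same amendment, reconcile the two lengths of survival follow-up (sections 4 and 7.1 against section 7.2.19), since they determine how long survivors are observed.
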